7 SAMPLE AND RECRUITMENT

7.1 Eligibility Criteria

7.1.1 Inclusion criteria

- 1. Age 18 years or older.
- 2. Intracranial intradural unruptured aneurysm.
- 3. Confirmed on angiogram (CTA/MRA/DSA).

4. Diagnosis of UIA between January 2006-December 2020.

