4 RESEARCH QUESTION/AIM(S)

Primary Aims:

Aim 1 - To validate the PHASES score in a UK population.

- Aim 2 To develop a new prediction model including all described predictors of risk.
- Aim 3 To report long-term risk of aneurysm rupture.

Secondary Aims:

Aim 4 – To develop risk models of aneurysm growth.

Aim 5 – To evaluate the efficacy of aneurysm screening regimens.

Aim 6 – To develop and evaluate new radiological predictors of aneurysm growth and rupture.

5 STUDY DESIGN and METHODS of DATA COLLECTION AND DATA ANALYIS

Data Collection – Baseline data – local neurosciences units Patients will be identified by members of the clinical care team and record:

- NHS number
- Name
- Date of birth
- Post code

These patients will be allocated a study number for pseudonymisation. This data will not be otherwise kept or used for other research purposes.

Further data will be collected from patient's case notes (either electronic or paper based as appropriate). A separate data definitions manual will be produced. All data collectors will be provided with a mandatory education module and correctly collect data from test cases before data collection.

The core covariates for each patient at time of diagnosis will be:

- Date of first diagnosis of aneurysm (date of first CTA/MRA/DSA or where not available date of first MDT or clinic appointment whichever is earlier)
- Date of inclusion in the study (date of first CTA/MRA/DSA or where not available date of first MDT or clinic appointment that lies within the unit's search period)
- Hypertension: a co-morbidity of hypertension or regular use of anti-hypertensive medication at time of diagnosis.
- Age: in years at time of diagnosis of aneurysm on angiographic imaging
- Gender:
- Site: anterior cerebral artery (including anterior communicating and pericallosal arteries), internal carotid (including bifurcation, ophthalmic, superior hypophyseal), MCA (including M1 segment and bifurcation), posterior communicating and posterior circulation (including vertebral, basilar, cerebellar and posterior cerebral arteries).
- Aneurysm size: the longest aneurysm dimension recorded to the nearest millimetre as described by the MDT discussion or where not available from the reporting radiologist at time of diagnosis or where not available from the clinic letter.
- Previous aneurysmal subarachnoid haemorrhage: confirmed diagnosis of aneurysmal SAH in the patient's medical history.

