- Population: European/North American, Finnish, Japanese (where race cannot be confirmed it will be assumed to be non-Finnish and non-Japanese on the basis that there is a low incidence of these populations in the UK and their presence would usually be considered noteworthy in a clinical note.

The additional desirable covariates at time of diagnosis will include:

- aspirin use any dose used >3* per week
- statin use any statin use >3* per week
- smoking history non-smoker, ex-smoker, current smoker
- Aneurysm multiplicity record number of intra-dural aneurysms the patient has (treated or untreated)
- Family history number of 1 first degree and second degree relatives with UIA/SAH
- History of Autosomal Dominant Polycystic Kidney Disease yes, no
- Aneurysm location subclassification ICA paraclinoid (ophthalmic and superior hypophyseal) ICA (PCom), ICA other (anterior choroidal and bifurcation), ACA ACOM, ACA pericallosal, MCA, Posterior (basilar termination), Posterior (SCA), Posterior (AICA) Posterior (PICA)
- Bleb or irregularity of aneurysm recorded as present or absent from radiology report only. If not mentioned in report assumed to be absent. If no radiology report available, then recorded as NA.
- New/known diagnosis: patients in whom the aneurysm was known prior to the search period will be recorded as known diagnosis and otherwise as new diagnosis.

Data collection – aneurysm rupture/censoring events – local neurosciences units

At the time of baseline data collection locally available follow up will be recorded which will include:

• Date of last follow-up

- Date of death (if applicable)
- Cause of death (if applicable)
- Date of SAH (if applicable)
- Location of aneurysm causing SAH (if applicable)
- Date of aneurysm treatment (if applicable)
- Reason for aneurysm treatment (if applicable)

This data will be used for quality control of subsequent HES searches.

Data collection - aneurysm rupture/censoring events - central HES ONS data

Upon collection of all baseline data, a search of the Hospital Episode Statistics (HES) and Office for National Statistics (ONS) databases using the patient's NHS numbers be conducted. The use of a HES and ONS search is designed to maximise the identification of rupture events which are not treated in neurosurgical unit as subarachnoid haemorrhage. It will thus identify events managed in a district general hospital or those who die pre-hospital.

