A new risk prediction model for rupture will be developed using the total data set, including the additional possible risk factors. The Cox regression model will be used for risk of rupture. The absolute risks can be estimated at relevant time intervals, 2, 5 and 10 years. Numbers of missing values will be summarised for each factor. Multiple imputation will be used to replace missing values. Discrimination of the final model will be assessed with the Harrell's c-statistic. Internal validity will be assessed by bootstrap resampling.

Additionally, the following sensitivity analyses will be performed:

In view that a significant number of aneurysms are anticipated to have grown and subsequently treated on follow up, any cases noted to have undergone treatment for aneurysm growth will be included in a model predicting the risk of rupture or treatment for aneurysm growth. In view that it is anticipated that a number of unexplained deaths will be captured where it will not be possible to resolve if the cause was SAH or not, a model predicting aneurysm rupture or unexplained or unattended death (R 96 and 98) will be built.

Statistical analysis - Aim 3 - Long term rupture rates

It is anticipated that initially follow up times will range from months to 15 years. This will be insufficient to definitively answer what the long term risks posed by aneurysms are. However, a model will be built including a term for new diagnosis vs known diagnosis. This will establish if rupture rates are similar between patients with new and prior diagnoses.

All patients, including those who underwent aneurysm occlusion, will be included in time-to-event analysis which will cover the whole duration of available follow-up. This will include Kaplan-Meier and proportional hazards models for univariate and multivariate survival curve fitting. A cumulative Hazard plot will be used to assess if rupture risk is constant or varies with time from diagnosis.

Longer term, HES searches will be repeated periodically using unique HES identifiers generated by DARS at the first HES search. These searches will identify any late events of SAH due to aneurysm rupture and models will be built to predict true long-term risk.

Data management

Patient confidentiality

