7.3 Recruitment

7.3.1 Sample identification

Patient identification

Due to most UIAs being detected during investigation for other conditions, HES coding for outpatient appointments cannot reliably identify patients with intracranial aneurysms and a local review suggested this may lead to a large underestimate of cases.

Therefore, patients will be identified by the direct clinical care teams at adult tertiary neurosurgical units in the UK treating patients with UIAs. All patients will be eligible whether seen in the centre, scanned in the centre or only discussed with the centre at MDT or on-call. Therefore, more than one search method may be applicable. Search methodology may be adapted to suit local case note and radiology records. We would recommend sequentially performing the following searches:

- 1. Electronic keyword searches of clinic letters, discharge summaries and MDTs. These capture most patients but risk missing patients not formally discussed with neurosurgery.
- 2. Electronic searches of cranial CTA, MRA and DSA reports for the term "aneurysm" excluding "no aneurysm". These searches capture all patients at the parent hospital but may miss regional patients scanned in district hospitals.
- 3. Searches of on call referrals may capture any further conservatively managed UIAs.

In some units, paper records of MDT or vascular clinics may be searched where electronic systems are not in place. Additionally, some units maintain prospective neurovascular databases which could be used for patient identification.

To reduce selection bias all participating centres will produce a written search strategy for their unit and perform a search over a locally prespecified time period. This period will be within the range of 1 January 2006 – 31 December 2020 (representing the implementation of PACS and the present), but may be shorter. The date of inclusion will be the date of the first document to identify the patient in that locally prespecified date range. Where aneurysms were diagnosed before the study dates, the aneurysm will be marked as "known diagnosis" and the date of inclusion remains that of the first document in the study date range.

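### Inclusion criterion 4 bars pre-2006 diagnoses that section 7.3.1 includes, and the time-from-diagnosis hazard plot needs delayed entry at inclusion for known cases

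*Protocol*

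**What the plan says.** **Eligibility.** Protocol section 7.1.1, criterion 4, requires "Diagnosis of UIA between January 2006-December 2020". Section 7.3.1 lets each unit choose its own search window: "This period will be within the range of 1 January 2006 – 31 December 2020", and it may be shorter. The same section then says: "Where aneurysms were diagnosed before the study dates, the aneurysm will be marked as" a known diagnosis, and "the date of inclusion remains that of the first document in the study date range". Section 5 defines the flag by the search window: "patients in whom the aneurysm was known prior to the search period will be recorded as known diagnosis".

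**Dates.** Section 5 collects two separate dates for each patient: "Date of first diagnosis of aneurysm", which is not limited to the search window, and a date of inclusion, which is.

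**Analysis.** For Aim 3, section 5 puts all patients into the time-to-event analysis and adds a new-versus-known term to a model. It also says: "A cumulative Hazard plot will be used to assess if rupture risk is constant or varies with time from diagnosis". Section 5 defines when follow-up ends. It does not define when it starts, and it does not mention delayed entry or left truncation.

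**The concern.** There are two linked problems.

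First, the two sections give opposite answers for a patient diagnosed before January 2006. Section 8.5 forbids enrolling anyone who fails the eligibility criteria, so a unit that follows section 7.3.1 for such a patient breaches section 8.5. The known group is also half of the Aim 3 contrast, and the background section criticises earlier studies for not separating new from prior diagnoses.

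Second, a known case enters only if the aneurysm is still unruptured (criterion 2) and untreated (exclusion 5) at inclusion. The interval from diagnosis to inclusion therefore cannot contain a rupture. If that interval counts as time at risk, the denominator grows and the numerator cannot. The rupture rate is then pulled down. The known group looks safer than the new group even when the two hazards are equal, which would read as risk falling with time since diagnosis. That is the question Aim 3 is meant to answer.

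**Working it through.** **1. Eligibility, side by side.** Take a patient diagnosed in 2003 whose first document in the search range is from 2008.

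- Criterion 4: diagnosis lies outside 2006-2020, so not eligible.
- Section 7.3.1: included in 2008 as a known diagnosis.

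The conflict holds whether the study dates in 7.3.1 mean the national range or the unit's own window, because 2003 precedes both. Its reach depends on the window:

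- Unit searching from January 2006: known means diagnosed before January 2006. Every such patient fails criterion 4, so no known cases remain.
- Unit searching 2012-2020: known cases diagnosed in 2006-2011 meet criterion 4 and remain. They carry the time-scale problem even if criterion 4 is enforced.

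**2. The plan's own rate (section 7.2.1).** The cited international cohort had 51 ruptures in 1,692 patients over 4.1 years.

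- Rate: 51 / (1,692 × 4.1) = 0.735% per year.
- For 60 events: 60/51 × 1,692 = 1,990.6 patients; × 4.1 = 8,161 years. The plan states 1,990 and 8,161, so its figures reproduce. The point disputes none of them.

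**3. Follow-up.** Pilot: 6,000 / 1,415 = 4.24 years per patient. The plan calls these years anticipated and does not say from which date they run. They are taken here as years after inclusion, which is an assumption.

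**4. Effect of counting from diagnosis without delayed entry.** Let f be the share of known cases and g their mean years from diagnosis to inclusion. The protocol gives neither, so both are assumed. Events are unchanged and mean person-time rises from 4.24 to 4.24 + f × g:

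ratio of naive to true rate = 4.24 / (4.24 + f × g)

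The formula was checked against a simulation of 400,000 patients per scenario. It used a constant hazard of 0.735% per year, exponential lead times and uniform censoring averaging 4.24 years after inclusion, with 5-year risk estimated by Nelson-Aalen on time from diagnosis. The true 5-year risk is 1 − exp(−5 × 0.00735) = 3.61%.

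| f | g (years) | f × g | Rate ratio | Naive rate per year | 5-year risk, no delayed entry | 5-year risk, delayed entry |
|---|---|---|---|---|---|---|
| 10% | 2 | 0.2 | 0.955 | 0.702% | 3.44% | 3.60% |
| 10% | 5 | 0.5 | 0.895 | 0.658% | 3.31% | 3.62% |
| 20% | 5 | 1.0 | 0.809 | 0.595% | 3.01% | 3.61% |
| 30% | 5 | 1.5 | 0.739 | 0.543% | 2.76% | 3.63% |

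The overall rate is therefore about 4% to 26% too low over these assumptions. Widening them to f = 5-30% and g = 2-10 years gives 2% to 41%. Delayed entry brings the 5-year risk back to the true value within simulation noise.

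**5. Known against new, true ratio 1.** The crude rate ratio becomes 4.24 / (4.24 + g): 0.68 for g = 2 and 0.46 for g = 5. The simulated values were 0.66-0.72 and 0.43-0.48.

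**The case against.** The strongest reply is that the protocol never says it will analyse known cases without delayed entry. Time from diagnosis is named once, for one plot. No time zero is set for the Kaplan-Meier or Cox models. Both dates that delayed entry needs are collected, and time origin is commonly settled in a statistical analysis plan, which is not at hand. This stands. A reader might infer that the plan commits an immortal-time error, but the documents support only a conditional risk: the one time scale named is wrong for known cases unless entry is delayed.

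It can also be said that the eligibility conflict is narrow, since shorter search windows leave known cases that satisfy criterion 4. That is right, so Aim 3 does not rest wholly on pre-2006 diagnoses. Nor do the documents show that units will in fact build different cohorts, because section 5 promises a data definitions manual and mandatory training. Neither argument removes the contradiction, and an analysis plan cannot repair an eligibility criterion.

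Two further inferences go too far. One is that all the false time falls in the early years: with exponential lead times averaging 5 years, exp(−1) = 37% of leads exceed 5 years, so later years are affected too. The other is that known cases, as survivors, cannot inform Aim 3. Late risk is by definition conditional on not having ruptured, and observing these patients from inclusion addresses it.

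Covariate timing is a fair remark, for example "Age: in years at time of diagnosis of aneurysm on angiographic imaging", since values may be old by the time a known case is included. Re-extracting them at up to 30 units would be a trade-off, not a correction.

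**Conclusion.** The contradiction between criterion 4 and section 7.3.1 is established from the text, for aneurysms diagnosed before January 2006. It should be removed because the two rules cannot both be followed.

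The time-scale point holds conditionally. If known cases are counted from diagnosis without delayed entry, rates are biased downwards and the new-versus-known comparison is biased towards a falling risk. The direction is certain. The size is not, because the share of known cases and their lead times are assumed and the 4.24 years rest on anticipated pilot follow-up read as time after inclusion. The 4-26% is an illustration, not an estimate for this cohort. The sample-size figures are unaffected.

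**What to change.** 1. Reword criterion 4 to require an unruptured aneurysm documented within the unit's search period, whether newly diagnosed or already known. Use the same reference period for the known flag in section 7.3.1 as in section 5.
2. State in the Aim 3 text that any analysis on time from diagnosis uses delayed entry (left truncation) at the date of inclusion.
3. Optional: a sensitivity analysis of Aim 1 in new diagnoses only.

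The cost is one eligibility sentence, one analysis sentence and the amendment approvals described in section 8. No new data are needed, since both dates and the new/known flag are already collected. The optional analysis gives up the known cases in that analysis only.

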7.1.2 Exclusion criteria

- 1. Mycotic or vasculitic aneurysms.
- 2. Aneurysm diagnosed on CT or MRI alone.
- 3. AVM associated flow aneurysms.
- 4. Extradural aneurysms (e.g. intra-cavernous).
- 5. Aneurysms previously treated by either microsurgical or endovascular techniques.
- 6. Small lesions uncertain as to whether they are truly aneurysmal ("dilatation", "bulge", 'Infundibulum", etc)

7.2 Sampling

7.2.1 Size of sample

Sample Size

There are no accepted methods for power calculation for validation studies of prognostic models. Therefore, usually the rule of thumb to have ten events for every covariate tested is applied.

For Aim 1, 6 covariates will be tested suggesting at least 60 SAHs will need to be captured. ISUIA recorded 51 ruptures in 1692 patients over 4.1 years. Sixty events may therefore be expected in 1,990 patients with 8,161 years of follow up.

For Aim 2, 120 events will need to be observed to account for the 6 additional commonly occurring covariates which would be expected in 3,981 patients with 16,332 years of follow up.

For autosomal dominant polycystic kidney disease (ADPKD) which has a low incidence, larger numbers of patients will be needed. Ten events in ADPKD are expected in 1360 patient years of follow up assuming the risk of SAH is not elevated and similar to the general population. However, 16,332 years follow up would only yield 195 years in patients with ADPKD (based on a population study which found 53/4436 IAs had ADPKD (Nurmonen 2017) and consistent with pilot data where 11/1025 cases examined to date had ADPKD). Therefore 113,905 years of follow up would be required to capture 10 ruptures amongst 1,340 years follow up in ADPKD patients. This would equate to 22,781 patients with 5 years of follow up (or applying the slightly looser rule of 5 events per prognostic factor this would require 56,952 years of follow up with 11,391 patients).

In a local pilot 1,415 cases were identified over 14 years in a population of 3 million with an anticipated 6,000 years of follow up. Extrapolating to England, Wales and Scotland 31,130 patients with 132,200 years follow up are available - well in excess of the target of 8,161 to validate PHASES in the general population, as well as the 16,332 to test the additional variables, but only just sufficient to answer the role of rarer predictors such as ADPKD. For reference PHASES was based on 29,166 years of patient follow up. Therefore, all cases that can be identified in England and Wales will be sought up to a maximum of 22,781.

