7.2.2 Sampling technique

All patients who are identified using the retrospective searches, and who meet the eligibility criteria, will be included. Sampling techniques to reduce this cohort size will not be used because rupture events are uncommon and sampling may lead to an underrepresentation of the true rupture rate if these patients are missed. Furthermore, the final cohort size needs to be as large a possible in order to accurately include uncommon prognostic factors such as APCKD in the final model.

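### The maximum of 22,781 patients assumes five years of follow-up each; the protocol's own projection of about 4.24 years gives about 8.5 rather than 10 ADPKD ruptures, and the maximum conflicts with Section 7.2.2

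*Protocol*

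**What the plan says.** Section 7.2.1 sizes the study by events per variable: "the rule of thumb to have ten events for every covariate tested is applied". The rupture rate comes from the international cohort: "ISUIA recorded 51 ruptures in 1692 patients over 4.1 years". For the rare predictor ADPKD, "Ten events in ADPKD are expected in 1360 patient years of follow up". The section scales this up by the share of aneurysm patients with ADPKD to 113,905 years of total follow-up and converts the result to patients: "This would equate to 22,781 patients with 5 years of follow up". The same sentence gives an alternative of five events per factor, needing 56,952 years.

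The next paragraph turns to feasibility. In the pilot, "1,415 cases were identified over 14 years in a population of 3 million with an anticipated 6,000 years of follow up". This is extrapolated to 31,130 patients and 132,200 years across England, Wales and Scotland, a total described as barely enough for rare predictors such as ADPKD. The paragraph concludes that "all cases that can be identified in England and Wales will be sought up to a maximum of 22,781". The Study Summary gives the same number as the planned sample size.

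Section 7.2.2 says that all identified patients who meet the eligibility criteria are included, that "Sampling techniques to reduce this cohort size will not be used", and that the cohort should be as large as it can be for the sake of uncommon factors such as ADPKD.

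**The concern.** Two adjacent paragraphs use different follow-up per patient: five years to set the maximum, and about 4.24 years to show that enough patients exist. If the second figure is right, the headline sample size does not deliver the target from which it was derived.

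The remark that the pool is barely enough refers to all 31,130 projected patients, yet the maximum drawn from it is 22,781/31,130 = 73% of that pool. Section 7.2.2 allows no maximum, and nothing says which patients would be left out if it were reached. The sentence setting the maximum names England and Wales only, although the projection includes Scotland and Section 5 plans a Scottish database search.

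At stake is the precision of the ADPKD effect in the Aim 2 model, the only target that drives the sample size to this level.

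**Working it through.** **Inputs, all from Section 7.2.1.** ISUIA: 51 ruptures, 1,692 patients, 4.1 years. ADPKD share: 53/4,436 in the cited population study, 11/1,025 in the pilot. Pilot: 1,415 cases, 6,000 anticipated years. Projection: 31,130 patients, 132,200 years.

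**Reproducing the plan's figure.**
- Rupture rate r = 51/(1,692 × 4.1) = 51/6,937.2 = 0.00735 per year.
- ADPKD years for ten ruptures = 10/r = 1,360.
- Total years = 1,360 × 16,332/195 = 113,905, as stated.
- Patients = 113,905/5 = 22,781, as stated.

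The maximum therefore follows from its inputs. The input in question is the five years.

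**Follow-up per patient in the protocol's own data.**
- Pilot: 6,000/1,415 = 4.24 years.
- National projection: 132,200/31,130 = 4.25 years.

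**What 22,781 patients give at 4.24 years.**
- Person-years: 22,781 × 4.2403 = 96,598. Ratio to plan: 4.2403/5 = 0.848, so 15% short.
- ADPKD years: 96,598 × 53/4,436 = 1,154.
- Expected ADPKD ruptures: 1,154 × 0.00735 = 8.5 (also 8.5 at 4.25 years).
- With the pilot prevalence: 96,598 × 11/1,025 = 1,037 years, and 1,037 × 0.00735 = 7.6 ruptures.

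**Patients needed for the stated target.** 113,905/4.2403 = 26,863, or 113,905/4.2467 = 26,822 on the national projection. Either is within the projected pool of 31,130.

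**What the whole projected pool would give.** 132,200 × 53/4,436 × 0.00735 = 11.6 ruptures, or 10.4 at the pilot prevalence. The full pool clears ten on either prevalence; 22,781 patients at pilot follow-up do so on neither.

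**Slips in the same section.**
- 120/r = 16,323 and 3,981 × 4.1 = 16,322, so the Aim 2 figure of 16,332 is ten too high. With 16,322 the total becomes 1,360 × 16,322/195 = 113,836, about 113,840 (22,767 patients at five years).
- The text gives both 1,360 and 1,340 ADPKD years. The stated total uses 1,360: 113,905 × 195/16,332 = 1,360.

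Neither slip changes the result materially.

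**The case against.** The strongest defence is that the sentence on 22,781 patients is a correctly computed conditional, and that 4.24 years is itself soft. The 6,000 years are anticipated, the pilot covered 14 years against a 15-year study window, and Sections 5 and 8.6 foresee repeat database searches that would add person-time to a fixed cohort. This stands in part: the shortfall concerns the first analysis, and a mean of five years would remove it at the population-study prevalence. But the protocol relies on the same 6,000 years for its feasibility claim and does not reconcile the two figures.

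Three stronger readings are tempting and are not supported.

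- **That the study is too small by its own rules.** Expected ADPKD ruptures of 7.6 to 8.5 meet the five-event alternative. The calculation also assumes that ADPKD does not raise rupture risk; any elevation would raise the count. The 96,600 person-years far exceed the 8,161 and 16,332 stated for Aims 1 and 2.
- **That the maximum discards 31,130 − 22,781 = 8,349 patients.** The documents do not show that it would be reached. Section 6 speaks of up to 30 units, Section 7.3.1 allows shorter local search periods, opt-outs are removed, and Section 7.3.2 refers to over 10,000 patients.
- **That the Aim 2 requirement omits covariates.** A reader might set "120 events will need to be observed to account for the 6 additional commonly occurring covariates" against the longer list in Section 5. Section 1, however, names exactly six examples besides polycystic kidney disease. Location subclass is a finer coding of site, which PHASES already includes; new or known diagnosis is assigned to the Aim 3 model; and gender is a core item, not one of the additional covariates. A miscount is not shown.

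**Conclusion.** The point holds in a limited form. Section 7.2.1 sets its maximum on an unsourced five years per patient, while its own pilot and projection imply 4.24 to 4.25. On those figures the stated size falls about 15% short of its person-year target and gives about 8.5 expected ADPKD ruptures (7.6 at the pilot prevalence) instead of ten. Separately, and whichever follow-up is right, a maximum contradicts Section 7.2.2; if it were reached, it would lower ADPKD precision.

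The size rests on three assumptions taken from the protocol: the ISUIA rupture rate, no excess rupture risk in ADPKD, and the anticipated pilot follow-up as the mean at the first analysis.

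**What to change.** State the ADPKD target in person-years: about 113,840 once 16,332 is corrected to 16,322 (113,905 as now written). Then do one of the following.

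1. Remove the maximum, which brings Section 7.2.1 into line with Section 7.2.2, and adjust the planned size in the Study Summary.
2. Keep 22,781, state that on pilot follow-up it gives about 96,600 person-years and 7.6 to 8.5 ADPKD ruptures at the first analysis, and amend Section 7.2.2 to acknowledge the maximum.

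In either case, make clear that the remark about bare sufficiency refers to the uncapped pool, reconcile the England and Wales wording with a projection that includes Scotland, and correct 1,340 to 1,360.

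The second option costs only a slightly less favourable stated figure. The first is a protocol amendment. It could enlarge a cohort whose identifiable data are used without consent under a requested section 251 waiver, so the ethics committee and the Confidentiality Advisory Group may need to be notified.

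### The person-years called available and just sufficient for ADPKD assume 14-year searches with full national coverage, which the design does not secure and the 22,781 cap contradicts

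*Protocol*

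**What the plan says.** Protocol section 7.2.1 starts from one unit: "In a local pilot 1,415 cases were identified over 14 years in a population of 3 million with an anticipated 6,000 years of follow up". It then scales up: "Extrapolating to England, Wales and Scotland 31,130 patients with 132,200 years follow up are available". The requirement for ADPKD is given as: "Therefore 113,905 years of follow up would be required to capture 10 ruptures amongst 1,340 years follow up in ADPKD patients". Set against that, the available total is described as "but only just sufficient to answer the role of rarer predictors such as ADPKD". The section converts the requirement to 22,781 patients at 5 years each, and offers a looser rule of 5 events (56,952 person-years, 11,391 patients). It ends by seeking all cases in England and Wales, with 22,781 as the maximum. The study summary gives 22,781 as the planned size.

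Section 7.3.1 has each centre prespecify its own search period within 2006-2020. Of that range it says: "representing the implementation of PACS and the present), but may be shorter". It gives no minimum length and does not say which years a shorter search should cover. Section 3 also describes the range as a maximum. Section 6 gives 30 units as an upper limit.

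**The concern.** A projection from one unit to the country needs two things to hold: every unit's catchment is included, and every unit searches as long as the pilot did. The sample-size section states neither condition, and other parts of the protocol relax both. This would matter little if the margin were wide, but the protocol itself calls it narrow. ADPKD is the predictor that sets the planned size, so if the person-years are not secured, the reason given for 22,781 is not secured either. A reader would then expect about 10 ADPKD ruptures where the design may deliver fewer.

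**Working it through.** **Inputs, all from 7.2.1.** Pilot: 1,415 cases, 14 years, 3 million people, 6,000 person-years. Rupture rate: "ISUIA recorded 51 ruptures in 1692 patients over 4.1 years", so 51/(1,692 × 4.1) = 0.735% per year. ADPKD share: 53/4,436 = 1.19%. Requirement: 113,905 person-years. Cap: 22,781 patients.

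**1. Reproducing the stated totals.**
- Patients: 1,415 × 22 = 31,130, exactly as stated.
- Person-years: 6,000 × 22 = 132,000, against 132,200 stated (ratio 22.03).
- Implied population: 3 million × 22 = 66 million.
- Requirement: 16,332 × 1,360/195 = 113,905, as stated.

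No term for search length or unit participation enters, so the pilot's 14 years and full coverage are built in.

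**2. Margin.** 1 − 113,905/132,200 = 13.8%. Expected ADPKD ruptures at 132,200 are 132,200 × 0.01195 × 0.00735 = 11.6, against a target of 10.

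**3. Shorter searches.** Actual windows are not in the protocol, so this is a range under assumptions:
- entry is uniform over a 14-year range;
- the exit rate λ is constant;
- the HES search falls 0-2 years after the range ends;
- only new diagnoses are counted;
- all units take part.

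A patient with potential follow-up f contributes (1 − e^(−λf))/λ. Setting the 14-year mean to the pilot's 6,000/1,415 = 4.24 years gives λ = 0.124, 0.152 and 0.173 for a lag of 0, 1 and 2 years. Person-years for a window of T years are 132,200 times the ratio of the integral of that contribution over the window to its integral over the full 14 years. A late window uses f from lag to lag + T. An early one uses f from lag + 14 − T to lag + 14.

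| Average window | Late: person-years (ADPKD ruptures) | Early: person-years (ADPKD ruptures) |
|---|---|---|
| 12 years | 103,000-108,000 (9.1-9.5) | 122,000-128,000 (10.7-11.3) |
| 10 years | 77,000-85,000 (6.7-7.5) | 107,000-117,000 (9.4-10.3) |
| 7 years | 42,000-53,000 (3.7-4.7) | 79,000-91,000 (6.9-7.9) |
| Break-even for 113,905 | 12.5-12.7 years | 9.6-10.9 years |

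Plain proportional scaling, with no follow-up model, gives a break-even of 14 × 113,905/132,200 = 12.1 years.

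**4. The cap, independent of search length.** At the pilot mean, 22,781 × 6,000/1,415 = 96,600 person-years, and 96,600 × 0.01195 × 0.00735 = 8.5 ADPKD ruptures. Reaching 113,905 at that mean needs 113,905/4.24, or about 26,860 patients. The cap yields 113,905 only at 113,905/22,781 = 5.0 years per patient.

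**5. What is not at risk.** Aim 1 needs 8,161 person-years and Aim 2 needs 16,332, at most 16,332/132,200 = 12% of the stated total. The 5-event rule (56,952) is met in every cell of the table except the 7-year late window, and by the capped cohort.

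**The case against.** The strongest reply is that the loss depends on where short windows fall. Follow-up runs to the HES search whatever the unit's window, and nothing says that short windows must be recent. This stands: early windows lose much less, and the 12.5-12.7 year break-even applies to late windows only.

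Next, section 7.3.1 also includes patients diagnosed before the window, dated from their first document within it. A late window therefore picks up earlier diagnoses still under follow-up, which the model leaves out. This stands too. If all such patients from earlier in the range were captured (an upper bound, assumed), late windows of 12 and 10 years would give about 128,000 and 117,000-118,000 person-years, both above 113,905.

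The protocol is also candid that the margin is narrow. It supplies a 5-event fallback and lists ADPKD among the desirable rather than the core covariates. That limits the consequence, but it does not make the stated total conditional.

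A reader might infer more than the documents support:
- **That 132,200 cannot be reached.** The range permits 15 years, and full 15-year searches everywhere would exceed 132,200 by about 9-11% before the cap is applied.
- **That the margin is really about 4%.** That uses the pilot's 11/1,025, which the protocol treats as consistent with 53/4,436.
- **That ineligible cases shrink the pilot base.** The gap between 1,415 identified and 1,025 examined does not show this.
- **That late-starting units can never inform 10-year risk.** The Aim 3 text and section 8.6 plan repeat HES searches, and the Aim 3 text concedes that initial follow-up is insufficient for long-term risk.

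**Conclusion.** The point holds in limited form: sufficiency for ADPKD is not assured, rather than shown to fail. The stated total is conditional on full coverage and 14-year searches, and sections 6 and 7.3.1 secure neither. A 13.8% margin is lost at an average window between about 9.6 and 12.7 years, depending on placement and HES lag under the model above. Capturing known diagnoses would soften the late-window loss.

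The conflict with the cap needs no assumption about windows. Section 7.2.1 counts 31,130 patients from three nations as available, then limits the cohort to 22,781 from two. At the pilot's own mean follow-up, that falls short of 113,905 by about 17,300 person-years (113,905 − 96,600). This assumes that the capped cohort has the pilot's mean. One weighted to early diagnoses would have a longer mean, but the protocol does not say how the cap would be applied.

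The stake is the 10-event ADPKD claim and the reasoning behind the planned size. The sizes set for Aims 1 and 2 are not affected.

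**What to change.** In 7.2.1:
- State that 132,200 person-years is conditional on full participation across England, Wales and Scotland and a 14-year search at each unit.
- Reconcile that figure with the England-and-Wales scope and the 22,781 cap, including the 5 years per patient behind the cap against the pilot's 4.24.
- Give person-years and expected ADPKD ruptures for a range of window lengths and placements, and update them once units have declared their windows.
- If fewer than 10 ADPKD ruptures are then expected, call the ADPKD estimate exploratory or rest it explicitly on the 5-event rule already stated.

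The cost is wording, a small table and a less favourable headline figure. Raising the cap, if that is how the conflict is resolved, would add abstraction work.

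Optionally, 7.3.1 could ask a unit that cannot search the whole range to prefer its earliest years. For equal patient numbers, an early 7-year window yields 1.5-2.2 times the person-years of a late one in the model above. The downside is that older records may be less complete, so this is a trade-off for the investigators and not a required change.
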